PROTOCOL

**Effect of *Lactobacillus rhamnosus* GG and
Bifidobacterium longum in children aged 3 to 5 years of
Villavicencio and Pasto.**

ClinicalTrials.gov ID: NCT03078179

Principal Investigator: [name]

Sponsor: Universidad Cooperativa de Colombia

Funded by: 1. Universidad Cooperativa de Colombia

2. Colgate

Version number: 5

17 June 2015

Adapt: 01 August 2016

Table of contents

1. Synopsis.....	2
2. Introduction	3
3. Schema	4
4. Schedule of activities.....	5
5. Study Description	6
6. Risk/Benefit assessment	7
7. Objectives and Endpoints.....	8
8. Study Design.....	10
8 Study Population	14
9 Study intervention.....	15
10 Statistical considerations	18
11. Regulatory, ethical, and study oversight consideration.....	20
12. References.....	21

1.Synopsis

Study Type	Interventional, Pilot Study
Intervention	
 1. Commercial Cow Milk with Probiotic (Lactobacillus rhamnosus and Bifidobacterium longum) 2. Commercial cow milk without probiotic
Study Design:	Repeated measures design.
Allocation:	Nonrandomized
Endpoint Classification	Efficacy Study
Intervention Model:	Crossover study
Masking:	No masking
Sample size	Convenience sampling
Primary Purpose	Treatment trial
Subjects:	Three to five-year-old children
Genders:	Both
Sites	Kindergarten in Villavicencio y Pasto, Colombia
Study duration	12 months
Objective	To determine the effect of consumption of commercial milk beverages enriched with Lactobacillus rhamnosus y Bifidobacterium longum on the incidence of caries in children aged 3 to 5 years.

[figure not shown]
2.Introduction

Several bacterial strains have been studied as probiotics, either isolated or in combination, as well as the doses used in studies, intervention periods, populations, experimental designs, and routes of administration. The results often include a decrease in *S. mutans* count in saliva or plaque, but few studies conduct dental clinical examinations to assess treatment. This is confirmed by a meta-analysis conducted by Laleman et al in 2013, claiming that the scientific evidence demonstrating caries control is insufficient (1). However, the results of studies describing the effect of probiotics in the index of carious lesions (2,3) or dental plaque, are promising (4,5).

The probiotics most commonly evaluated so far in the oral cavity are isolated microbial strains, mainly of the digestive tract, like the ones belonging to the genus *Lactobacillus* (*L. rhamnosus*, *L. reuteri*, *L. casei*, *L. brevis*, *L. paracasei*, *L. acidophilus*, *L. plantarum*) and *Bifidobacterium* (*B. bifidum*, *B. longum*, *B. lactis*, *B. animalis*, *B. infantis*) (6,7). These bacteria have proven their safety for many years, allowing clinical studies and the development of commercial products, with the added value that some have been identified in healthy individuals (DMF = 0) (*L. rhamnosus*, *L. plantarum*, *L. acidophilus*, *L. brevis*, *L. paracasei*) (8), suggesting their role in micro-ecologic balance.

One of the most commonly studied probiotic bacteria in the oral cavity was isolated by Gorbach and Godin in 1983 from digestive tract of a healthy adult (9). It was named *Lactobacillus rhamnosus* GG (ATCC53103) and is characterized by inhibiting, by means of bacteriocins, a wide variety of human pathogenic bacteria (10), including *S. mutans*, *S. sobrinus*, *Aggregatibacter actinomycetemcomitans*, *Porphyromonas gingivalis* and *Prevotella intermedia*. In addition, this bacterium colonizes the microcosm of saliva, and has no cariogenic effect. This bacterium was used to conduct one of the most complete clinical studies in children (aged 1 to 6 years), reducing the incidence of caries in the age of 3 to 4 years (2).

3.Schema

4. Schedule of activities

Activities	Months											
	1	2	3	4	5	6	7	8	9	10	11	12
Parents meeting	■											
Informed consent		■										
Personal interview		■										
Clinical diagnosis			■									
Selection criteria			■									
Begin: diagnostic tests				■								
Intake milk without probiotic for 3 months				■	■	■						
Ending: diagnostic tests							■					
Intake milk with probiotic for 3 months							■	■	■			
Ending: diagnostic tests										■		
Analysis of information											■	■

5. Study Description

Brief Summary: The objective of this study is to determine if the presence of bacteria with probiotic characteristics (*Lactobacillus rhamnosus* GG and *Bifidobacterium longum*) in a commercial milk, control some measures that indicate cariogenic processes. **Detailed Description:** Dental caries is a disease caused by a shift in pH balance, resulting in the formation of a biofilm composed mainly of cariogenic microflora. The interaction between this microflora and host factors conditions the deceleration or acceleration of the disease. Some biotechnology tools have been tried based on all this research, including probiotics, intended for a selective control of the etiological agents of caries and the maintenance of oral homeostasis. **Methodology:** In this study, preschool children belonging to public kindergarten in Villavicencio and Pasto, Colombia will be invited to participate. After obtaining parent's informed consent, the children will start commercial milk intake without probiotic for 3 months (*Klim fortificada Nestlé*). One week after, they will start commercial milk with probiotic during others 3 months (*nanPro3 Nestlé*). Clinical and microbiological testing of saliva at baseline, 3 m, and 6m will be performed. Differences in salivary pH (before and after a sugar solution), remineralization and demineralization in early Stage Decay and Established decay tooth (according to ICDAS) and quantification of Streptococci of the mutans group. **Expected results:** Statistically significant decrease in pH drop, demineralization in decay tooth and quantification of Streptococci of the mutans group.

6.Risk/Benefit assessment

Minimal Risk:

This study has a minimal risk because the probability and magnitude of possible harms implied by participation in the research is no greater than those encountered by participants in the aspects of their everyday life that relate to the research (TCPS Chapter 2B). The intervention is safe because the study will use two commercial milk with Sanitary Registry of health products. During the reconstituting of powdered milk, the person responsible will use bottled water and good hygienic conditions. Moreover, during the clinical diagnostic and the clinical laboratory, this research will practice principles and practice about biosafety.

Benefit:

The immediate potential benefits of this research with children, is the daily intake of two nutritive commercial milk, for 6 months. Also, the researcher gives information about the oral health, the presence of caries, and the requirements of specific treatment.

7.Objectives and Endpoints

OBJECTIVES	ENDPOINTS	Justification for endpoints
To determine the effect of consumption of milk beverages enriched with Lactobacillus rhamnosus and Bifidobacterium longum in diagnodent measurement.	Diagnodent measurement of tooth decay lesions (ICDAS 1-4). The idea is to compare the effect of probiotics in children during the intake of milk without probiotic versus during the intake of milk with probiotic.	DIAGNOdent is a laser fluorescence device used for dental caries diagnosis in occlusal and smooth surfaces. Diagnodent measurement allows knowing if the effect of probiotic suppresses the demineralization of the cariogenic lesion. The reason is, if the probiotic inhibit the cariogenic bacteria, reduce the demineralization and improve the mineralization
To determine the effect of consumption of milk beverages enriched with Lactobacillus rhamnosus and Bifidobacterium longum in the change of pH of saliva after a rinse with sugar.	For this objective, the purpose is to compare the points difference between salivary pH before and after a rinse with sugar, in children during the intake of milk without probiotic versus during the intake of milk with probiotic	The scientific literature shows when there are many cariogenic bacteria, the drop of Ph after a rinse with sugar is greater compared with people who have less cariogenic bacteria levels.
To determine the effect of consumption of milk beverages enriched with Lactobacillus rhamnosus y Bifidobacterium longum in the concentration of group mutans streptococci in saliva.	The comparison of the quantification of group mutans streptococci from saliva, during the intake of milk without probiotic versus during the	Other studies have shown the inhibition of Lactobacillus rhamnosus in Streptococcus mutans .

	intake of milk with probiotic	
To determine the effect of consumption of milk beverages enriched with Lactobacillus rhamnosus y Bifidobacterium longum in dental plaque index.	The comparison of dental plaque index during the intake of milk without probiotic versus during the intake of milk with probiotic, show us if Lactobacillus rhamnosus and Bifidobacterium longum reduce the formation of dental plaque.	Other studies, showed that some probiotics reduce the dental plaque.

8. Study Design

7.1 Hypothesis

1. The commercial milk beverages enriched with *Lactobacillus rhamnosus* and *Bifidobacterium longum* reduce the demineralization of caries lesion (ICDAS 1-4).
2. The commercial milk beverages enriched with *Lactobacillus rhamnosus* and *Bifidobacterium longum* reduce the change of salivary pH after a rinse with sugar.
3. The commercial milk beverages enriched with *Lactobacillus rhamnosus* and *Bifidobacterium longum* reduce the quantification of mutans streptococci in saliva.
4. The commercial milk beverages enriched with *Lactobacillus rhamnosus* and *Bifidobacterium longum* reduce the dental plaque.

7.2 Study design: Nonrandomized comparison, single group assignment, controlled before and after study.

7.3 Arm treatment information:

- A. Experimental: Commercial Cow Milk with Probiotic. 200 ml of commercial nutritive milk fortified with probiotic *Lactobacillus rhamnosus* and *Bifidobacterium longum* once a day.
- B. Placebo comparator: Commercial Dairy Cow Milk 200 ml of commercial nutritive milk without probiotic, once a day.

7.4 Dosing and administration:

Experimental: 200 ml of commercial nutritive milk fortified with probiotic *Lactobacillus rhamnosus* and *Bifidobacterium longum* (Nan Pro3, Nestlé) once a day.

Placebo comparator: 200 ml of commercial nutritive milk without probiotic (Klim Fortificada Nestlé), once a day.

7.5 Study intervention duration:

3 months intake the placebo comparator, and 3 months intake the experimental treatment.

7.6 Sites:

Kindergarten in Villavicencio, Colombia

Kindergarten in Pasto, Colombia

7.7 Phase of the trial:

1. Invitation to participate in the trial: at the kinder garden during a meeting, the researchers invite parents to participate.
2. To request the informed consent of the parents of the children.
3. Diagnosis, selection, and collection of samples. Each child will be informed of the process in a simple way.

First Day:

- 3.1 First selection: the dentist checks up the oral health condition. Children without caries or with advanced caries will not continue in the process. Children who enter the criteria continue in the process.
- 3.2 Second selection: Clinical assessment of demineralization with Diagnodent, after of dental prophylaxis. The children with measure upper to 7, are included.
- 3.3 ICDAS: dentist with calibration in ICDAS take this measure.

Second day:

- 3.4 Index dental plaque Sillness and Löe.
- 3.5 Collection of saliva: Each child will accumulate saliva and then collect it in sterile containers (approximately 1.5-2 ml).
- 3.6 1 ml of saliva with glycerol (10%) will be frozen (-20°C) in microcentrifuge tubes (1.5ml). This sample is for microbiological analysis of *S. mutans*.
- 3.7 With the other 1ml is to determine the pH. The Salivary pH will be determined with pHmeter Fisherbrand Accumet Portable AP110.
- 3.8 Rinse with 10% sugar solution. The children will make a mouthwash with sugar solution and they will wait 5 minutes. Finally, the pH of the saliva is will be determined again.

4. Microbiological Analysis of *S. mutans*

The 100µl of saliva sample will be dilute with 900µl of sterile normal saline. Then will be performed decimal dilutions of saliva were made up to 10⁻³. 100µl of every dilution will be uniformly spread in Agar Mitis Salivarius with tellurium and bacitracin. Finally, the plates will be incubated via anaerobically system with 5% CO₂ for 48 hours at 37°C. The confirmation of morphology of the bacterial colonies will be determined under a stereo microscope. Also, the CFU will be count under the stereomicroscope.

5. Interview with the parents to know the information about the children (state of health, diet, teeth brushing frequency)

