6. INTERVENTION

Children were given 200 mL of milk with after the breakfast every day, for five days a week. First, the children will drink milk without probiotic, during the 3-months period. And then the children drink milk with probiotic during the 3-months period (*L. rhamnosus* and *B. longum*). The nursery school staff prepared the commercial milk with researcher supervision. The milk will be prepared with safe water (packaged water).

6. After the intervention with each milk, the next outcome measures:

6.1 Index dental plaque Sillness and Löe.

6.2 Collection of saliva: Each child will accumulate saliva and then collect it in sterile containers (approximately 1.5-2 ml).

6.3 1 ml of saliva with glycerol (10%) will be frozen (-20°C) in microcentrifuge tubes (1.5ml). This sample is for microbiological analysis of *S. mutans*).

6.4 With the other 1ml is to determine the pH. The Salivary pH will be determined with pHmeter Fisherbrand Accumet Portable AP110.6.5 Rinse with 10% sugar solution. The children will make a mouthwash with sugar

solution and they will wait 5 minutes. Finally, the pH of the saliva is will be determined again.

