6.6 Dental prophylaxis

6.7 ICDAS

6.8 Clinical assessment of demineralization with Diagnodent.

8 Study Population

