8.3 Exclusion criteria

- Children with systemic disorders who need special care and/or who have the intolerance to milk drinks or allergy to any of the components of the experimental and/or the placebo beverage.
- Children who don't like milk.
- Children with severe decay

8.4 Lifestyle consideration:

The children's parent will inform when:

- The child uses antibiotic
- The child visits another dentist and the dentist use Fluor.
- The child uses an antiseptic or mouthwash.
- The child improves the brush frequency.

9 Study intervention

Primary Outcome Measure:

1. Change in remineralization of tooth decay

DIAGNOdent peak reading in three moments, at the beginning and at the end of the milk without probiotic (after 3 months), and at the end of the milk with probiotic (after 3 months) (Table 1).

Secondary Outcome Measures:

1. Change of salivary pH after a rinse with sugar.

Change pH after a rinse with sugar (point of difference), in three moments, at the beginning and at the end of the milk without probiotic (after 3 months), and at the end of the milk with probiotic (after 3 months) (Table 1).

2. Change of Dental Plaque Index

Silness-Löe plaque index in three moments, at the beginning and at the end of the milk without probiotic (after 3 months), and at the end of the milk with probiotic (after 3 months) (Table 1).

3. Change of concentration of group mutans streptococci in saliva

Colony Forming Units (CFUs) determination in three moments, at the beginning and at the end of the milk without probiotic (after 3 months), and at the end of the milk with probiotic (Table 1).

TABLE 1.

Variable	Scale of measurement	Data	Type of variable	Measure Type	Measure of dispersion
BEFORE (Control and Intervention)					
Diagnodent measurement	Quantitative	Values 0-99	Dependent	-Mean -Median	-Standard deviation -Inter-Quartile range
Change of salivary pH after a rinse with sugar.	Quantitative	Point of difference	Dependent	-Mean -Median	-Standard deviation -Inter-Quartile range
Dental Plaque Index	Qualitative	0=absent 1=present	Dependent	Frequency	NA
Colony Forming Units of the group mutans streptococci	Quantitative	UFC	Dependent	-Mean -Median	-Standard deviation -Inter-Quartile range
AFTER (Control and Intervention)					
Diagnodent measurement	Quantitative	Values 0-99	Dependent	-Mean -Median	-Standard deviation -Inter-Quartile range

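### Baseline plaque, salivary mutans and sugar-challenge pH are measured after a dental cleaning but the follow-up measures before it, so any contrast using baseline mixes cleaning status with the milk effect

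*Combined protocol and SAP*

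**What the plan says.** Section 7.7 sets the order of measurement twice.

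- **Baseline (step 3).** On the First Day, after the visual screen (3.1), step 3.2 is "Clinical assessment of demineralization with Diagnodent, after of dental prophylaxis", followed by ICDAS (3.3). The Second day starts with the plaque index (3.4), then "3.5 Collection of saliva: Each child will accumulate saliva and then collect it in sterile containers" and the rest of the saliva work: the mutans sample (3.6), resting pH (3.7) and pH after the sugar rinse (3.8).
- **After each milk (the second step numbered 6).** Under "After the intervention with each milk, the next outcome measures" the list starts with "6.1 Index dental plaque Sillness and Löe", goes on to saliva, pH and sugar rinse (6.2-6.5), and only then reaches "6.6 Dental prophylaxis", ICDAS (6.7) and DIAGNOdent (6.8).

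On the use of baseline, section 5 states "Clinical and microbiological testing of saliva at baseline, 3 m, and 6m will be performed". Section 9 titles every secondary outcome as a change and gives it three moments; for plaque, for example, "Silness-Löe plaque index in three moments, at the beginning and at the end of the milk without probiotic", plus the end of the probiotic milk. Table 1 has a before block and an after block. Section 7, on the other hand, describes the plaque endpoint as "The comparison of dental plaque index during the intake of milk without probiotic versus during the intake of milk with probiotic", and the null hypotheses H02-H04 are also worded as one milk against the other.

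Section 11 (Statistical analysis) names the paired t-test, the Wilcoxon test and, for plaque, McNemar's test. It does not name the two moments that each test compares.

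**The concern.** The three moments of each secondary outcome are not measured under like conditions. Baseline follows a study cleaning. The 3- and 6-month values are taken before that visit's cleaning, about 3 months after the previous one.

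For plaque the effect is direct, because a prophylaxis removes what the index scores. For mutans counts and the pH drop it is an inference: less plaque may mean fewer cariogenic bacteria and a smaller drop, but the documents give no effect of cleaning on either.

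Because the tested pair is not named, a contrast that uses baseline remains open. Such a contrast would attribute part of the cleaning effect to a milk. The direction depends on the contrast chosen: a change from baseline makes either milk look harmful, and a comparison of the two changes makes the probiotic look helpful.

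**Working it through.** **Inputs from the documents.** Step order: section 7.7, steps 3.1-3.8 and 6.1-6.8. Significance level 0.05: section 11 (taken as two-sided; sidedness is not stated). Plaque coded absent or present: Table 1. The plan gives no sample size, power or error rate, so there is no figure to reproduce.

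**Assumptions, because the documents are silent.** Number of children n = 20 to 60; within-child correlation rho = 0.3 to 0.7; cleaning effect d; share of children with plaque when not recently cleaned, 50% to 90%; no milk effect and no time effect.

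**Step 1, bias.** Let B, M3 and M6 be the baseline, 3-month and 6-month values, scored so that higher is worse (for pH, the size of the drop). Cleaning lowers B by d.

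| Contrast | Bias | Direction |
|---|---|---|
| M3 - B | +d | against the control milk |
| M6 - B | +d | against the probiotic milk |
| (M6 - M3) - (M3 - B) | 0 - d = -d | towards the probiotic |
| M6 - M3 | 0 | none |

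The third row applies to pH and mutans only. McNemar's test compares two binary readings and does not test a difference of changes.

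**Step 2, pH and mutans (paired t, unit variance, noncentral t).** SD(M6 - B) = sqrt(2(1 - rho)) and SD of the difference of changes = sqrt(6(1 - rho)). The noncentrality is d × sqrt(n) / SD. For n = 40 and rho = 0.5 the SDs are sqrt(1) = 1 and sqrt(3) = 1.73. With d = 0.2 the noncentralities are 0.2 × 6.32 / 1 = 1.26 and 0.2 × 6.32 / 1.73 = 0.73 in absolute value.

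| d (SD) | M6 - B, n = 40, rho = 0.5 | M6 - B, all n and rho | Difference of changes, n = 40, rho = 0.5 | Difference of changes, all n and rho |
|---|---|---|---|---|
| 0.1 | 9.5% | 6.5-16.6% | 6.5% | 5.5-8.8% |
| 0.2 | 23.5% | 11.1-50.3% | 11.0% | 7.0-20.6% |
| 0.5 | 86.9% | 43.4-99.8% | 42.9% | 17.9-81.0% |

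M3 - B gives the same figures as M6 - B. M6 - M3 stays at 5%.

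**Step 3, plaque (exact McNemar, 20,000 simulated trials, latent correlation 0.5), baseline versus 6 months.** Each range runs over 50% to 90% plaque-positive.

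| Baseline lowered by | n = 20 | n = 40 | n = 60 |
|---|---|---|---|
| 10 points | 3-5% | 13-18% | 19-31% |
| 20 points | 18-20% | 48-64% | 70-85% |

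For 3 versus 6 months the rate is 0.1% to 3% throughout.

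**Step 4, how large d could be.** First Day and Second day are labels without an interval. The schedule in section 4 puts clinical diagnosis and selection in month 3 and the start-of-study tests in month 4. The gap could be one day or several weeks; if weeks, d could be near 0.

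**Step 5, the primary outcome.** DIAGNOdent follows prophylaxis at baseline (3.2) and after each milk (6.6, then 6.8). Its three moments match in this respect.

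**The case against.** The strongest reply is that the stated comparison is not touched. Section 7 and H02-H04 set one milk against the other, which is most naturally 3 versus 6 months. Both of those readings precede their visit's cleaning and follow a study cleaning about one milk period earlier. No section specifies a test against baseline, and Table 1 lists variables and summary measures, not tests. This stands, and it is why the point is minor. It does not remove the point, because section 9 still defines each outcome as a change over three moments that include baseline, and section 11 leaves the pair open.

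A second reply is that every size above is assumed, and that for pH and mutans even the existence of a cleaning effect is inferred. That stands too. At n = 20 a 10-point fall in plaque produces no inflation at all. The order after each milk also rests on step numbering, not on an explicit statement.

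A reader might infer something stronger: that the mismatch hides a time trend in the control period, which is then read as a probiotic effect at 6 months. The documents do not support that. No trend check is planned, and M3 - B would not be a clean one even with d = 0, because it also contains any effect of three months of control milk. That M6 - M3 carries any time trend follows from the single-group fixed sequence (7.2) and is a separate matter.

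**Conclusion.** The mismatch is in the text and holds for plaque index, salivary mutans and sugar-challenge pH. Any contrast that uses their baseline values is biased by the cleaning effect: +d for a change from baseline, and -d for a difference of changes in pH or mutans. The size is unknown. The rates above illustrate a range of assumed n, d, correlation and plaque frequency and are not estimates for this trial.

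Two wider conclusions might be drawn, and neither follows. The documents do not show that the tests of H02-H04 are biased, since their natural reading, end of control milk versus end of probiotic milk, has zero bias from this source. Nor is the primary DIAGNOdent result affected. Severity is minor: these are secondary outcomes of a pilot, the effect depends on an analysis that is left open but not specified, and d may be small.

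**What to change.** **If baseline is not yet collected:** use the follow-up order. After the visual screen (3.1), take the plaque index, saliva and sugar rinse, and only then do the prophylaxis, DIAGNOdent and ICDAS. No new procedure is needed. The cost is samples from children who then fail the DIAGNOdent screen. No failure rate is given; with a share f failing at that step, 40 included children mean 40f/(1 - f) extra sample sets, or about 4, 10, 17 and 40 for f = 10%, 20%, 30% and 50%.

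This equalises the order within a visit but does not make baseline fully comparable. A reordered baseline would still not follow a study cleaning about 3 months earlier. If that raised B by e, M3 - B and M6 - B would be biased by -e, so the limitation should be stated.

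**If baseline is already collected:** state in section 11 that H02-H04 are tested only as end of control milk versus end of probiotic milk. Report the interval from prophylaxis to the baseline plaque, saliva and pH measures. Label baseline contrasts for these three outcomes as supportive, with the mismatch stated. This costs about a sentence each.

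### No outcome reading is masked, although the CFU count on stored saliva could be masked cheaply and the chairside readings in part

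*Combined protocol and SAP*

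**What the plan says.** The masking entry in the Synopsis (section 1) declares that there is none. Section 7.2 gives the design as "Nonrandomized comparison, single group assignment, controlled before and after study".

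The order is the same for all children. Section 7.7, under Intervention, says "First, the children will drink milk without probiotic, during the 3-months period", followed by "And then the children drink milk with probiotic during the 3-months period". Section 5 sets the assessments: "Clinical and microbiological testing of saliva at baseline, 3 m, and 6m will be performed". Only the 6-month assessment follows the probiotic milk. Section 5 also gives the result the study hopes for: "Statistically significant decrease in pH drop, demineralization in decay tooth and quantification of Streptococci of the mutans group".

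The readings differ in kind:

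- **CFU (secondary).** Step 3.6 of section 7.7 stores the specimen: "1 ml of saliva with glycerol (10%) will be frozen (-20°C) in microcentrifuge tubes (1.5ml"). In step 4 a person confirms colony morphology under a stereomicroscope, and "Also, the CFU will be count under the stereomicroscope".
- **DIAGNOdent (primary).** Section 9 specifies a "DIAGNOdent peak reading in three moments". Step 6.8 takes it at the visit, after prophylaxis.
- **Plaque index (secondary) and ICDAS.** Both are scored on the child at the same assessment (steps 6.1 and 6.7). Step 3.3 mentions calibration for ICDAS, but masking is mentioned for no measure.
- **Salivary pH (secondary).** Read with a pH meter.

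Nursery staff prepare the milk, and a researcher supervises them. Section 11 (Statistical analysis) plans paired t-tests, Wilcoxon tests where data are not normal, and McNemar's test for plaque, at p below 0.05.

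**The concern.** Serving the milk openly does not require reading the outcomes openly. Confirming and counting colonies involves judgement, and the plan neither hides the visit from the person who counts nor keeps earlier values from the examiner.

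The design makes this more serious than it would be in a trial with randomised order. There, a drift in reading between visits would fall on both milks. Here the visit and the milk coincide, so a tendency to read the last visit lower works in one direction for every child, and that direction is the one the plan expects. Pairing removes stable differences between children, but it does not remove a shift tied to a visit. At stake is whether a significant fall in CFU, or in a chairside score, could be told apart from a reading effect.

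**Working it through.** The plan states no sample size, SD, effect size or power, so there is no figure of its own to reproduce. The check has three steps.

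**1. How a reading shift enters the comparison.** Let Y0, Y3 and Y6 be a child's readings at baseline, 3 and 6 months, and let d be a reading shift at 6 months. Section 11 does not say which paired contrast is tested, so take both natural candidates:

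- Y6 − Y3: the expected value is milk effect + time effect + d.
- (Y6 − Y3) − (Y3 − Y0): Y6 again has coefficient 1, so d again enters once, in full.

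Pairing cancels none of d, and more children shrink the standard error but not d.

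**2. What that does to the test.** Assume no milk or time effect, and a shift of b SDs of the paired difference. The paired t statistic is then noncentral t with n − 1 degrees of freedom and noncentrality b√n. The two-sided rejection rate is P(|T| > t(0.975, n − 1)). From the plan: the 5% level and the paired t-test. Assumed: two-sided testing, n and b.

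For b = 0.2 the noncentrality is 0.2 × √20 = 0.89 at n = 20 and 0.2 × √100 = 2.00 at n = 100. Rejection rates under a true null:

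| n | b = 0 | b = 0.1 | b = 0.2 | b = 0.3 | b = 0.5 |
|---|---|---|---|---|---|
| 20 | 5.0% | 7.1% | 13.6% | 24.7% | 56.5% |
| 30 | 5.0% | 8.3% | 18.5% | 35.5% | 75.4% |
| 50 | 5.0% | 10.7% | 28.4% | 54.8% | 93.4% |
| 100 | 5.0% | 16.8% | 50.8% | 84.4% | 99.9% |

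Nothing in the documents locates this trial in the table. It shows only that a modest shift matters, and matters more as n grows.

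**3. Which readings can be masked under the plan as it stands.**

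- *CFU.* The tubes are stored, so child and visit can be hidden by a code before plating. There is one complication. The schedule of activities puts the three test rounds in months 4, 7 and 10. Holding every tube to the end would leave baseline saliva frozen about 6 months longer, and 3-month saliva about 3 months longer, than 6-month saliva. Any loss of viable bacteria in storage would then differ by visit. Keeping frozen time equal avoids this but means plating visit by visit, so the date reveals the visit even when tubes are coded. Counting coded plate images later, in mixed order, resolves it.
- *DIAGNOdent, ICDAS, plaque.* These are read on the child, with no stored specimen. All children are on the same milk at a given visit, so an examiner who knows the order knows the milk. Withholding earlier values prevents anchoring on them, and withholding the order helps, but neither gives full masking.
- *pH.* A meter reading, with less room for judgement.

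**The case against.** The strongest reply is that this is a declared open, nonrandomised pilot. Milk is wholly confounded with time, so perfect masking would still not make the milk comparison valid. That is correct and limits the gain: masking removes a separate, avoidable bias and leaves the larger one in place.

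A reader might infer that all the operator-dependent readings, including the primary outcome, could be masked. The documents do not support that. Only CFU can be properly masked. The primary DIAGNOdent reading is taken live under one fixed order. The documents describe it as a laser fluorescence reading on a 0–99 scale and say nothing of operator influence, so how far it is open to a reading shift is itself an assumption.

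A reader might also infer that masking needs no extra staff. Staffing is not given, so this cannot be checked. It is plausible for labels and charts, and less certain for an examiner or technician unaware of the order. Nor does preparation by nursery staff keep the research team unaware of the milk, since a researcher supervises it and may also be an assessor.

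Finally, no individual reader's expectation is documented. The statement of expected results belongs to the plan as a whole, and there is only one probiotic assessment per child. The documents do not show that any reading would be biased, only that nothing guards against it. What stands is that codable specimens are to be read uncoded without a reason given.

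**Conclusion.** The point holds, mainly for a secondary outcome. No masking is planned. The CFU count is a manual reading of stored saliva and can be masked cheaply, and the chairside readings can be masked in part. Under the fixed order, a reading shift at 6 months biases the paired difference by its full amount.

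The size is unknown. For an assumed shift of 0.2 SD of the paired difference, the false-positive rate of the 5% test is about 14% (n = 20) to 51% (n = 100); over the wider range of assumptions examined it runs from 7.1% to 99.9%. These figures rest on assumed n, an assumed shift, two-sided testing and a true null with no time effect. They illustrate the mechanism and do not estimate the bias in this trial. The change is a worthwhile low-cost improvement. It does not rescue the comparison between the milks.

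**What to change.** Change the masking entry in the Synopsis to open milk with masked outcome reading where possible, and add to section 7.7:

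1. **CFU.** Label saliva tubes and plates with random codes that hide child and visit, with the key held by someone who does not count. Keep the time frozen before plating equal across visits. Where plates are run visit by visit, photograph them and count the coded images in mixed order.
2. **DIAGNOdent, ICDAS and Silness-Löe plaque index.** Give the examiner a fresh chart at each visit, showing what to read but no earlier values. Where existing staffing allows, do not tell the examiner the milk order.
3. **Separation of roles.** The researcher who supervises milk preparation does not examine children or count colonies.
4. **Stated limitations.** The chairside readings are only partly masked, because the visit can be inferred. Masking does not remove the confounding of milk with time.

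The cost is coded labels, fresh charts, a code key to keep and, if images are used, photographing the plates. Whether the separation of roles needs another person depends on staffing that the protocol does not describe. Milk, visit schedule and statistical tests are unchanged.
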